Protocol Title: Motor Evoked Potential and Cortical Silent Period in Migraine

Document Date: October 3, 2025

İSTİNYE UNIVERSITY CLINICAL RESEARCH ETHICS BOARD RESEARCH PROTOCOL

1. Open title of the study: Investigation of Motor Evoked Potential and Cortical Silent Period in Migraine Patients

Basis and rationale for the study (Explain in detail): Migraine is a neurological disease that reduces individual quality of life and creates a significant economic burden on healthcare systems worldwide. While the pathophysiology of migraine has not been fully elucidated, recent research indicates that this disease is associated not only with vascular but also with neurological and cortical changes (Goadsby et al., 2017). There is increasing evidence of increased excitability and impaired inhibitory mechanisms, particularly in central nervous system regions such as the motor cortex (Coppola et al., 2007).

Transcranial magnetic stimulation (TMS) is a non-invasive and reliable neurophysiological method that examines muscle responses by stimulating the motor cortex. Parameters such as the motor evoked potential (MEP) and the cortical silence period (CSP) obtained with this method are used to measure motor cortex excitability and inhibitory control, respectively (Chen et al., 1999). CSP is widely used, particularly in the assessment of GABA-B-mediated inhibitory mechanisms. The hypothesis of decreased cortical inhibition in migraine patients is an important research question that can be tested with CSP measurements.

Some previous studies have reported findings such as shortened CSP duration and increased MEP amplitudes in migraine patients, which may indicate a state of cortical hyperexcitability (Brighina et al., 2002; Afra et al., 1998). However, these findings are not consistent, and how they differ across different subtypes of migraine (with or without aura) has not yet been fully elucidated.

Therefore, this study aims to reveal the changes migraine causes in cortical physiology using objective and quantitative methods, filling gaps in the literature and contributing to clinical assessments. Furthermore, by examining the relationship between these parameters and clinical characteristics such as migraine type, duration, and attack frequency, it is aimed to take a first step toward establishing individualized neurophysiological profiles.

1. The main purpose of the research, any secondary purposes (Explain in detail):

Primary Objective:

The primary objective of this study is to evaluate the level of inhibitory control in the motor cortex in migraine patients using objective and non-invasive methods. For this purpose, comparisons will be made between individuals with migraine and healthy controls by measuring Motor Evoked Potential (MEP) and Cortical Silence Period (CSP) parameters obtained with Transcranial Magnetic Stimulation (TMS). CSP duration has the potential to directly measure the effect of migraine on cortical inhibition, particularly because it is used in the assessment of GABA-B-mediated inhibitory mechanisms (Chen et al., 1999).

Secondary Objectives:

1. Motor output analysis: Peristimulus Time Histogram (PSTH) and Peristimulus Frequencygram (PSF) analyses will be applied to electromyographic signals to evaluate the temporal order

and frequency changes of motor unit responses after TMS. While PSTH analyzes the post-stimulation timing of individual motor units; PSF more sensitively displays the frequency change after stimulation (Türker & Powers, 2001). These analyses can reveal the reflection of cortical stimulation at the spinal level and its effect on motor output in more detail.

2. Biomarker potential: The potential use of TMS-based parameters such as CSP and MEP as biomarkers for the pathophysiology of migraine will be evaluated. This will aim to develop objective neurophysiological measures that can contribute to future diagnostic and therapeutic processes.

1. Expected benefits of the study:

At the end of this study, objective data on the inhibitory capacity of the motor cortex in migraine patients are expected to be obtained. TMS parameters, particularly cortical silence period (CSP) and motor evoked potential (MEP), can be used to understand the neurophysiological basis of migraine. These data offer the following potential contributions: They will contribute to a better understanding of the balance of cortical excitability and inhibition in the pathophysiology of migraine. The CSP and MEP data obtained may form the basis for the development of objective diagnostic biomarkers for migraine in the future. The study results may indicate the presence of cortical dysfunction in individuals with migraine and support the development of personalized treatment approaches. Evaluation of changes in motor output using electrophysiological methods such as PSTH/PSF, included in secondary analyses, can provide a more holistic understanding by demonstrating how the network from the cortical to the spinal level is affected. This study, in which volunteers did not undergo any invasive procedures, offers a non-invasive, safe, and reproducible research approach.

2. Research method (Explain in detail):

Participants:

The study will include individuals aged 18–45, right-handed, and previously diagnosed with migraine. Migraine will be diagnosed according to the diagnostic criteria of the International Headache Society (IHS).

Data Collection Method:

This study will be conducted using surface electromyography (sEMG) and needle EMG methods, combined with non-invasive brain stimulation (TMS). Transcranial magnetic stimulation (TMS) will be applied to the motor cortex during both resting and voluntary muscle contraction. Simultaneously with TMS application, muscle responses will be recorded via surface EMG electrodes. Additionally, single motor unit (SMU) recordings will be made for more detailed analysis of motor neuron activity. For SMU recordings, needle EMG will be performed using special needles (approximately 70 µm in diameter, 25G) with sterile tips and Teflon-coated copper wire. After the needle is inserted into the FDI (first dorsal interosseous) muscle, it will be withdrawn, leaving only the wires inside. The curved tip of these wires, resembling a fishhook, facilitates their insertion into the muscle. After the needle is inserted, the subject will be asked to forcefully contract the target muscle several times, ensuring the wires are inserted into the muscle. This method allows monitoring the activity of a single motor neuron even during movement. All EMG signals will be collected using CED (Cambridge Electronic Design, UK) systems. EMG signals will be amplified using a CED 1902 four-channel amplifier (MKIII) and then digitized using a CED 3601 Power 1401 MKII

DAC unit. Recorded data will be analyzed using Spike2 7.20 software. SMU recordings will be taken in bipolar format, and the signals will be amplified 1,000-10,000 times. The signals will then be passed through a 200 Hz high-pass filter and digitized at a 20,000 Hz sampling rate.

Methods and Devices to be Used:

Transcranial Magnetic Stimulation (TMS) Application:

TMS applications will be performed using the Magstim 200² Monophasic Stimulator (Magstim Company Ltd, UK). A 70 mm diameter figure-of-eight (butterfly-type) double-ring coil is preferred for stimulation.

1. Specify which of the following is the research design:

Observational Studies

- A. Descriptive research (case series are included in this group)
- B. Case-control studies (retrospective)
- C. Cross-sectional studies, surveys are included in this group)
- D. Cohort studies (prospective)
- E. Historical cohort studies

2. Experimental Studies

- A. Controlled trials
 - I. Parallel controlled
 - a. Randomized
 - b. No randomization
 - II. Sequential Controlled
 - a. Self-controlled
 - b. Cross-over controlled
 - III. Externally controlled
- B. No control group

3. Meta-analyses

2. The number of patients and volunteers to be included in the study, and their characteristics (age ranges, gender, handedness, etc.).

In this study, the primary unit of analysis for measurements is not the "participant," but rather the motor unit activity. Since temporal and frequency analyses will be conducted by taking multiple motor unit measurements from each individual, the primary data is the motor unit count.

Nevertheless, for procedural reasons, the study plans to include a total of 20 volunteers (10 migraineurs, 10 healthy controls). Both groups will be matched for age and gender.

- Age Range: 18–45 years
- Gender: Both male and female participants will be included; however, due to the higher prevalence of migraine in women, the proportion of female participants may be higher.
- Handedness: Only right-handed individuals will be included.
- Diagnosis: The migraine group will consist of individuals who have been diagnosed with migraine for at least one year according to IHS criteria.

3. Method for determining the number of volunteers to participate in the study and sampling method: (Where and how will the samples be obtained, and how will the selection be made in the clinic?)

The total sample size was determined based on previous similar studies and power analyses, taking into account the level of efficiency and significance ($\alpha = 0.05$, power = 80%).

A minimum of 10 participants was anticipated for each group.

Purposive sampling will be used as the sampling method.

- **Migraine Group:** Individuals followed in neurology outpatient clinics and previously diagnosed with migraine will be included in the study if they are informed about the study and agree to volunteer.
- **Control Group:** Individuals with no history of neurological disease will be selected from university staff and students, matched by age and gender.

4. List the inclusion and exclusion criteria for the study: Inclusion Criteria:

Inclusion Criteria:

- Being between 18 and 45 years old
- Right-handed
- Having been diagnosed with migraine for at least 1 year (for the migraine group)
- Being a healthy individual without a migraine diagnosis (for the control group)
- Having signed a written informed consent form
- Having at least a primary school diploma (to be able to understand instructions))

Exclusion Criteria:

- History of epilepsy or seizures
- Presence of another neurological or psychiatric disease

- Having a metal implant, pacemaker, or similar conditions that contraindicate TMS
- Pregnancy
- Having previously experienced serious side effects from TMS or EMG
- Drug or alcohol addiction
- Severe visual or hearing impairment

5. If there is a control group, please describe its size and characteristics, and where and how it will be recruited:

Control group, migraine The study will consist of 10 healthy volunteers without a diagnosis of migraine. These individuals will be matched to the migraine group based on age, gender, and handedness. Individuals participating in the control group will be selected from among university staff and students through a volunteer call by the research team. Their eligibility will then be verified through a neurological assessment and brief medical history. The control group will be subjected to the same measurement protocol as the migraine group (TMS, EMG), allowing for objective comparisons between the two groups.

6. Tests, relevant laboratory, and other examinations to be performed:

Name of test or examination to be performed: Cortical Silence Period (CSP) measurement, Motor Evoked Potential (MEP) measurement, Surface Electromyography (sEMG) recording, Needle Electromyography (EMG), Motor unit analysis (analyzed with Spike2 software)

Name and surname of contact person: [name]. [name]

Address: The research was conducted at the Translational Dentistry Research Laboratory at the Faculty of Dentistry, İstanbul Gelişim University. This laboratory has the technical infrastructure to perform transcranial magnetic stimulation (TMS), surface and fine-wire EMG recording, and data analysis using Spike2 software.

[contact]

7. What are the risks and process issues that may be encountered during the study? If you have any precautions or a plan B, please explain.

Possible Risks:

- Transient headache, dizziness, and occasional muscle twitches due to TMS application

Process Issues:

- Lack of participant cooperation
- Artifact formation during muscle activity
- Device stability issues due to laboratory temperature

Precautions:

- Detailed information and informed consent will be obtained from all participants.
- Participant comfort will be ensured before each test.
- Devices will be checked with pre-tests.
- Sessions will be canceled and rescheduled if necessary.

8. Which parameters, tests, and methods to be used in the study are routine and which are specific to the study:

Routine Applications:

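### The objectives make the between-person CSP/MEP comparison primary and motor-unit analysis secondary, but the sizing section makes motor units the primary unit and primary data

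*Protocol*

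**What the plan says.** **Objectives.** Under Primary Objective, the protocol states that "comparisons will be made between individuals with migraine and healthy controls by measuring Motor Evoked Potential (MEP) and Cortical Silence Period (CSP) parameters". Under Secondary Objectives, item 1 is "Motor output analysis: Peristimulus Time Histogram (PSTH) and Peristimulus Frequencygram (PSF) analyses will be applied to electromyographic signals". The section on expected benefits confirms the ranking: "Evaluation of changes in motor output using electrophysiological methods such as PSTH/PSF, included in secondary analyses". The Data Collection Method section introduces single motor unit recordings as an addition to surface EMG.

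**Sizing.** The item on the number of patients and volunteers says "the primary unit of analysis for measurements is not the 'participant,' but rather the motor unit activity". It gives the temporal and frequency analyses as the reason and concludes, from "taking multiple motor unit measurements from each individual, the primary data is the motor unit count". It then adds that "for procedural reasons, the study plans to include a total of 20 volunteers (10 migraineurs, 10 healthy controls").

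The next item, on how the number was determined, says "The total sample size was determined based on previous similar studies and power analyses", with alpha 0.05 and power 80%, and "A minimum of 10 participants was anticipated for each group". It names neither the outcome nor the unit to which the 80% applies.

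**Analysis and termination.** For group comparisons, section 11 lists an independent-samples t-test or Mann–Whitney U test. Its only repeated-measures method is tied to a time-by-group effect. Section 10 allows early termination if too little motor unit data can be obtained.

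**The concern.** The same data are secondary in the objectives and primary in the sizing section. The temporal and frequency analyses cited in the sizing section are what secondary objective 1 describes as PSTH/PSF. A reader therefore cannot tell which result answers the study's question, or what the power statement refers to.

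Two things are at stake. First, if this is left open until data are in hand, either analysis could be presented as primary. Second, several motor units from one person are correlated. If the motor unit is the unit of analysis and units enter an independent-samples test as separate observations, the standard error is too small and a false migraine–control difference becomes more likely than 5%.

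**Working it through.** **Step 1: can the sizing wording be read consistently with the objectives?** The phrase about measurements in the sizing sentence could confine it to how recordings are counted. But the sentence sets the motor unit against the participant and rejects the participant. The paragraph then calls the motor unit count the primary data and brings in the 20 people as a procedural matter. Even on the mild reading, data that the objectives call secondary are called primary.

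**Step 2: the protocol's own sample size.** Inputs from the protocol are 10 per group, alpha 0.05 (sidedness not stated) and power 80%. It shows no effect size or SD, so the 10 cannot be reproduced; the formula can only be inverted for the detectable standardised difference d, with the participant as unit.

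- Normal approximation, two-sided: d = (1.960 + 0.842) × √(2/10) = 1.25
- Noncentral t, two-sided: d = 1.32
- Noncentral t, one-sided: d = 1.16
- Power of the two-sided t-test at 10 per group: about 40% for an assumed d of 0.8 and about 56% for d of 1.0

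**Step 3: what happens if motor units are the unit and are entered as independent.** The number of units per person (m) and the intraclass correlation (ICC) are assumptions; the protocol gives neither. The design effect is DE = 1 + (m − 1) × ICC.

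- m = 5, ICC 0.3: DE = 1 + 4 × 0.3 = 2.2, so 50 units per group carry the information of 50/2.2 = 22.7 independent values
- m = 10, ICC 0.5: DE = 1 + 9 × 0.5 = 5.5, so 100 units per group carry that of 100/5.5 = 18.2

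Type I error was simulated under a normal random-intercept model: no group effect, 10 people per group, and a unit-level two-sided t-test at 0.05, with 200,000 replicates per setting.

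| Units per person | ICC 0.1 | ICC 0.3 | ICC 0.5 |
|---|---|---|---|
| 3 | 0.074 | 0.125 | 0.172 |
| 5 | 0.098 | 0.190 | 0.267 |
| 10 | 0.155 | 0.314 | 0.415 |

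The large-sample approximation 2 × [1 − Φ(1.96/√DE)] agrees: 0.186 for m = 5, ICC 0.3, and 0.403 for m = 10, ICC 0.5. Unit-level Mann–Whitney tests (8,000 replicates) gave 0.070 to 0.405 over the same grid. At a lower ICC of 0.05 the t-test error is milder, about 0.05 to 0.11.

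A t-test on one mean per participant gave 0.050 in all nine settings of the table. The problem is therefore the unit, not the test.

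**The case against.** The strongest reply is that the sizing paragraph is qualified. It speaks of the unit for measurements and explains itself by the temporal and frequency analyses, so primary data may mean only the basic recordings of that analysis. It never names PSTH/PSF as the primary outcome and never demotes CSP or MEP. This softens the conflict, but the express rejection of the participant as the primary unit remains, and no statistical analysis plan could follow both statements.

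Other points stand in part:

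- **Every stated count is of people.** True: no motor-unit target appears. What is unsettled is the outcome and unit behind the 80% power, not the head count.
- **The inflated error is conditional.** True. It needs the strong reading of the sizing section and unaveraged units in an independent-samples test. Section 11 does not say this will happen, it also lists regression where needed, and per-participant summaries could be specified in an analysis plan that is not shown. The fault is the contradiction, not the absence of that detail.
- **The inputs are assumed.** True. With few units and a low ICC the excess is small: about 0.056 at 2 units and ICC 0.05. The figures above 0.3 should not set the seriousness of the point.
- **The 1.32 SD figure would remain after rewording.** True. It contradicts no stated figure; it shows what the head count supports once the participant is the unit.
- **The section 10 clause is permissive.** True. It does not itself contradict a secondary role for motor units, and section 10 also has a general criterion for technically inadequate measurements. It needs only a consequential check.

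**Conclusion.** The concern holds. The protocol gives two incompatible accounts of what is primary, and this rests on its wording alone. It should be corrected before any data are seen.

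The practical size depends on which account is followed. Under the objectives, the comparison is 10 versus 10 people, with 80% power only for about 1.32 SD two-sided (1.16 SD one-sided). Under the sizing section, with units pooled as independent, the nominal 5% error becomes about 7% to 41% for 3 to 10 units per person and ICC 0.1 to 0.5, and about 5% to 11% at ICC 0.05. Confidence is high for the contradiction. The inflation is a conditional consequence resting on assumed inputs.

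**What to change.** Make the objectives, the expected-benefits section and the sizing section name the same primary outcome and unit.

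- **If the objectives stand,** replace the sizing wording with, for example: *The primary unit of analysis is the participant. Motor-unit (PSTH/PSF) measures are secondary and are analysed with units clustered within participant, by per-participant summaries or a mixed model.*
- **If motor units are meant to be primary,** change the objectives and the expected-benefits wording instead, and still account for clustering within participants.
- **In either case,** tie the alpha 0.05 and 80% power statement to the chosen outcome and unit, and reconcile the two grounds given for 20 volunteers (procedural reasons and power analyses). Then check that the section 10 clause on insufficient motor unit data fits the chosen primary outcome.

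The cost is mainly rewording, with no new measurements. The power statement needs slightly more: the effect size and SD behind it, or a plain statement that 10 per group is set by feasibility. On the stated objectives, the investigators would also have to accept that motor-unit results are secondary and that 10 per group supports 80% power only for about 1.32 SD.
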